3. OBJECTIVES AND ENDPOINTS

Objectives	Endpoints
Part 1: Dose Escalation	
Primary	

 Determine RP2D and schedule of GSK3368715 administered orally to participants with advanced stage solid tumors 	
 Incidence of DLT Incidence and severity of adverse events
Secondary	

 Evaluate the preliminary clinical activity of GSK3368715 	
 Best overall response

 Characterize the PK of GSK3368715, including the PK in the fed and fasted state in the food effect sub-study 	
 PK parameters (Cmax, Tmax, AUC, others) PK parameters (Cmax, Tmax and AUC) in the fed and fasted state in the food effect sub-study
Part 2: Dose Expansion	
Primary	

 Evaluate the preliminary clinical activity of GSK3368715 	
 Objective response rate (ORR)
Secondary	

 Characterize the safety of GSK3368715 administered at the RP2D and schedule to participants with DLBCL, pancreatic cancer, NSCLC, and bladder cancer 	
 Incidence and severity of adverse events

 Further evaluate the clinical activity of GSK3368715 	
 Progression-free survival (PFS)

 Characterize the PK of GSK3368715 	
 PK parameters (Cmax, Tmax, AUC, others)
Part 1 and Part 2	
Exploratory	

 Evaluate time to response (TTR), duration of response (DOR) and overall survival (OS) Evaluate changes in PD biomarkers relevant to define the molecular mode-of-action of GSK3368715 Investigate biomarkers such as, but not restricted to, MTAP deficiency and CDKN2A gene deletion, as potentially predictive of sensitivity or resistance to GSK3368715 Characterize the relationship between PK, PD, and clinical activity of GSK3368715 Evaluate the relationship of pharmacogenetic profile in host DNA and response to GSK3368715 therapy Determine the impact of GSK3368715 on function and health-related quality of life Determine the amount of GSK3368715 excreted in urine from participants in the 	

PK/PD expansion cohorts

- Characterize the metabolic profile of GSK3368715 (in the PK/PD expansion cohorts)
- Investigate biomarkers such as, but not restricted to, D-dimer, fibrinogen and Factor VIII to evaluate whether GSK3368715 affects the coagulation cascade

4. STUDY DESIGN

4.1. Overall Design

This is a first time in human (FTIH), open-label, repeat-dose, non-randomized, multicenter study to evaluate the safety, tolerability, PK, PD, preliminary clinical activity and establish a recommended dose of GSK3368715 in participants with refractory/relapsed solid tumors and DLBCL.

The study will consist of a dose-escalation phase, including at least one PK/PD cohort and a food effect cohort, (Part 1) and dose expansion phase (Part 2):

- **Part 1:** GSK3368715 doses will be escalated using the Neuenschwander continual reassessment method (N-CRM). The populations enrolled will be participants with selected solid relapsed/refractory tumors. Based on safety and tolerability, and the PK/pharmacodynamic characteristics of the molecule, recommended Phase 2 (RP2D) dose(s) and schedule(s) will be established.
- **Part 2:** the safety and preliminary clinical activity of GSK3368715 administered at the RP2D and schedule will be further evaluated in two expansion cohorts
 - **Expansion Cohort 2A:** Participants with relapsed/refractory Diffuse-large B-cell lymphoma (DLBCL)
 - **Expansion Cohort 2B:** Participants with selected relapsed/refractory solid tumors where MTAP deletion occurs at a frequency of approximately $\geq 25\%$ (e.g., pancreatic, bladder, and non-small cell lung cancer).

Note: In both expansion cohorts, both MTAP proficient and deficient participants will be enrolled. Separate analysis will be conducted for MTAP deficiency or MTAP proficiency/wild type within each specific disease histology.

Based on the emerging safety- and molecular activity profile of GSK3368715 combination regimens with novel, active agents such as the small-molecule PRMT5 inhibitor, GSK3326595 and/or with approved oncology therapies may be considered. Rationale for these future combinations will be provided before the initiation of that combination and added by way of a protocol amendment.

The study includes a screening period, an intervention period and follow up. Participants will be screened for eligibility beginning approximately 4 weeks before the start of

intervention. Participants may continue treatment in the study until disease progression, unacceptable toxicity, or withdrawal of consent. For participants who discontinue intervention prior to a determination of PD, the follow-up period includes disease assessments every 8 weeks until documented PD. Following PD or for participants that discontinue study intervention, participants will be contacted every 12 weeks to assess survival status for 2 years from the start of the study. Participants with confirmed partial response (PR) or complete response (CR) will be followed for response duration.

Assessment of disease status will be performed by the Investigator in accordance with Response Evaluation Criteria in Solid Tumors (RECIST) v1.1 and the latest version of Lugano Criteria for NHL.

4.1.1. Part 1: Dose-Escalation Phase

Cohort Size: The initial dose cohort(s) will include up to three participants per GSK3368715 dose level. Cohorts will be expanded at the first instance of a \geq Grade 2 drug-related non-hematological toxicity. From there on, a minimum of 3 and a maximum of 12 DLT evaluable participants may be assigned to any single dose at the discretion of the Dose Escalation Committee (DEC) as outlined in the Dose Escalation Plan.

Replacement: If a participant fails to receive at least 75% of the planned doses within the 21-day DLT observation period for reasons other than toxicity (e.g., concurrent illness or disease progression), the participant will be replaced by additional participant(s) assigned to the same dose level and will not be counted as DLT evaluable.

Dose Escalation: After each dose cohort, a dosing recommendation for the next cohort will be made using the Neuenschwander Continual Reassessment Method (N-CRM) [[Neuenschwander, 2008](#)].

The N-CRM design makes use of a Bayesian logistic regression model relating dose and toxicity and is expected to locate the target dose level efficiently while minimizing the number of participants exposed to pharmacologically inactive or unsafe dose levels. The N-CRM method is fully adaptive and makes use of all DLT information, therefore is expected to locate the target dose level efficiently.

The N-CRM estimates, for each potential dose, the posterior probabilities that the DLT rate lies in each of four toxicity ranges:

- A dose falls in the **Under-dosing** range if the probability of a DLT at the dose is, 16%.
- A dose falls in the **Target** Toxicity range if the probability of a DLT at the dose is $\geq 16\%$ and $< 33\%$.
- A dose falls in the **Excessive** Toxicity range if the probability of a DLT at the dose is $\geq 33\%$, and $< 60\%$.
- A dose falls in the **Unacceptable** Toxicity range if the probability of a DLT at the dose is $\geq 60\%$

At the time of each dose-escalation decision, the dose with the highest posterior probability of lying in the Target Toxicity range will be the model-recommended dose for

the next cohort. Additionally, the following constraints for the recommended dose will be maintained:

- The posterior probability of the DLT rate lying in the Excessive Toxicity or Unacceptable Toxicity range is less than 25%.
- VTE safety rules
 - Upon re-initiation of enrolment under Protocol Amendment 3, details of a VTE meeting the DLT criteria are given in Section 4.1.3 and in Table 6.
- Upon re-initiation of enrolment under Protocol Amendment 3 at 100mg , dose escalation steps will be considered in maximal steps of 50 mg, depending on the pharmacodynamic effects and the safety profile observed in previous cohorts, taking into consideration the updated DLT criteria (see Table 6).
- *Note:* GSK3368715 dose de-escalation is also possible using this method.

An updated posterior estimate of the dose-toxicity curve will also be provided at the time of the dose-escalation meeting. Further details about the N-CRM approach are provided in Section 9. Although the N-CRM will be used to recommend the next dosing level, the DEC (i) will review all available data, including safety, PK and PD data from current and prior cohorts, (ii) can halt or reduce the GSK3368715 dose based on clinical judgement at any time during the trial, and (iii) can recommend alternative schedule(s) if emerging data suggest that continuous daily dosing will result in excessive toxicity or limited efficacy (Section 4.1.4). *Note:* if an alternative schedule is evaluated, the starting dose at the time of a schedule change will be the dose for which the target toxicity level was not exceeded using once daily dosing schedule.

Dose Schedule: GSK3368715 will be dosed initially orally (po) Based on emerging safety-, PK-, and PD- data, the DEC may recommend to evaluate alternative dosing schedule(s). The starting dose for an alternative dosing schedule will not exceed the highest GSK3368715 dose declared safe by the DEC at the time of the proposed schedule change.

During dose escalation, the first dose will be staggered by at least 24 hours between the participants enrolled within a cohort. This staggered dosing start is not required for participants enrolling at previously cleared doses.

PK/PD/Metabolite/Biomarker-Cohort: At GSK3368715 dose levels near to the expected RP2D, the DEC may recommend to expand a cohort(s) to up to 12 participants for additional PK- and PD-, metabolite- and/or biomarker-sample collection.

Under protocol amendment 03, a 100mg PK/PD cohort will be opened on resuming enrolment, and a 50mg PK/PD cohort may be opened in parallel. An additional PK/PD cohort may be opened later at a different dose level. The total maximal number of participants enrolled on PK/PD cohorts will be approximately 30.

The DEC may mandate to:

- (1) take pre- and post-dose tumor biopsies,

- (2) collect additional urine-, plasma-, and/or whole blood samples, and/or
- (3) perform ¹⁸F-fluorodeoxyglucose (FDG) positron emission tomography (PET) (i.e. FDG-PET)/computer tomography (CT) (PET/CT) scan assessments. in the additional participants enrolled in these GSK3368715 cohort(s).

The intention is to generate more comprehensive data at therapeutically relevant GSK3368715 dose level(s) in order to (i) establish a dose-response curve for GSK3368715 on the basis of PD-biomarkers, (ii) further characterize the metabolism of GSK3368715, and/or (iii) investigate the molecular mode-of-action of GSK3368715 on the basis of exploratory biomarkers. Participants may be enrolled into these PK/PD/Metabolite/Biomarker cohort(s) even after the MTD and/or RP2D has been identified and study Part 2 has been initiated.

Maximum-tolerated Dose: MTD is the highest GSK3368715 dose that emerges from the evaluation of safety-, PK-, and PD-data guided by the N-CRM statistical design during the DLT evaluation period.

Recommended Phase 2 Dose: RP2D of GSK3368715 will be determined after review of all available safety-, PK-, PD-, and clinical efficacy data in accordance with the N-CRM design. The RP2D will be equivalent with the MTD or a lower GSK3368715 dose that provides adequate PK exposure and biologic activity with superior tolerability.

Note: If necessary, alternate dosing schedules can be explored to determine additional biologically active doses even after a RP2D is defined.

4.1.1.1. Food effect Cohort

Once a RP2D is identified, a food effect sub-study may be initiated. It will be an open-label, randomized, single dose, two period, cross over study to investigate the effect of a high-fat, high-calorie meal on the bioavailability of GSK3368715 with a tablet formulation at or near the RP2D. Initiation or completion of this sub-study is not required prior to initiating part 2. GSK3368715 dosing (fed then fasted, or fasted then fed) will be separated by at least 3days. A minimum of 12 participants in the United States may be enrolled in the sub-study. A participant requiring dose reduction or discontinuation from study before completion of at least 48 hours after dosing in fasted/fed state in the sub-cohort will be replaced by a new participant. All participants enrolled to the sub-study, on completion of their participation in this segment of the study, will continue on a daily dosing schedule until discontinuation criteria are met, as described in Section 7.1.

The food effect sub-study will be open to participants with histologically- or cytologically confirmed solid malignancies as described for Part 1 in Section 5.1.

The high-fat (approximately 50% of the total caloric content of the meal), high-calorie meal (approximately 800 to 1000 calories) will be the representative example given by the 2002 US Food and Drug Administration (FDA) guidance [FDA, 2002]. Additional details of the required meal will be provided in the SRM.

Participants enrolled in the sub-study will be assigned to one of two sequences, as described in [Table 5](#); equal numbers will be assigned to each sequence. The schedule of visits for participants enrolled in the sub-study is detailed in [Table 4](#) in Section 1.3. Upon completion of the sub-study, all participants will continue to undergo scheduled assessments as described in [Table 2](#). Additional details, including the process of sequence assignment, will be provided in the SRM.

Table 5 Food Effect Sub-Study

Food effect cohort (single dose administrations)			
Sample size	Sequence	Period 1 (W1D1)	Period 2 (W1D4/D5)
6	1	Fasted	Fed
6	2	Fed	Fasted

Fasted: Participants should take nothing by mouth apart from water and other medications for at least 8 hours prior to dosing and should continue fasting until at least 4 hours after administration of the morning dose. Participants should be administered the drug product with 240 mL (8 fluid ounces) of water. Water will be allowed as desired except for one hour before and after drug administration. Participants will receive standardized meals approximately 4 and 10 hours post dose.

Fed: Following an overnight fast (at least 8 hours), participants should start the recommended high fat, high calorie breakfast 30 minutes prior to administration of the drug product. Study participants should eat this meal in 30 minutes or less; however, the drug product should be administered 30 minutes after start of the meal. The drug product should be administered with 240 mL (8 fluid ounces) of water. No food should be allowed for at least 2 hours post-dose. Water will be allowed as desired except for one hour before and after drug administration.

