1. The assessments required at the treatment discontinuation visit (TDV) must be completed within 30 days from the date that study intervention was discontinued and must occur prior to the start of subsequent anti-cancer therapy; the window for this visit is +10 days

Table 4 Schedule of Activities (SoA) (Food effect cohort)

Food effect cohort (Section 4.1.1.1); samples collected in this section are in addition to any samples, studies, and visits described in Table 2) ³									
	D1	D2	D3	D4	D5 ⁴	D6	D7	D8	D9 and beyond
Administer study drug ¹	X				X				←-----daily dosing----->
Plasma PK samples ²	X	X	X	X	X	X	X	X	X ³

1. Study drug should be administered in fed or fasted state, based on assignment as described in Section 4.1.1.1
2. PK samples on Days 1 and 4/5 should be collected at 0 (pre-dose), 0.25h ± 5 min, 0.5h ± 5 min, 1h ± 5 min, 1.5h ± 5 min, 2h ± 10 min, 3h ± 10 min, 4h ± 10min, 6h ± 30 min, 8h ± 30 min, 12h ± 2h, 24± 2h, 48± 2h and 72± 2h hours post dose
3. Refer to Table 2 for subsequent PK sample requirements
4. In order to accommodate clinic schedules, the Day 5 dosing (including all PK assessments) may be performed one day earlier (on Day 4), i.e. Days 5 to 8 would shift to Days 4 to Day 7, and then all subsequent PK assessments from then on would follow the same schedule as in Table 2

NOTE: Participants in the food effect sub-study are subject to all screening, safety, PK, and efficacy evaluations detailed in Table 1 and Table 2. Samples collected in this section are in addition to any samples collected in Table 2, with the exception of Day 1-8 PK collections, in which the time points in Table 4 supersede those in Table 2

[figure not shown]
Any participant who experiences vomiting at or between 0.25-3 h will be removed from statistical analysis of PK comparability between fasted/fed state

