2.2.1.5. Clinical Pharmacology of GSK3368715

Pharmacokinetics (PK) of GSK3368715 is currently being evaluated after administration of single and repeat daily oral administration of GSK3368715 at doses of 50mg to 200mg in study 207675. Concentrations are detected in plasma 0.25 hours after oral administration with peak concentrations at around 1.0 hours on average, then GSK3368715 declines bi-exponentially with a mean terminal elimination half-life of 20-24 hours. A dose dependent increase in plasma exposures (both C_{max} and AUC) of GSK3368715 were observed as doses increased from 50mg QD to 200 mg QD. Following multiple-dose administration, mean AUC was up to 2-4 fold higher on Day 15 as compared to Day 1 in all dose groups, except for participants ^{PPD} and ^{PPD} who showed much higher accumulation on Day 15 of 6-7 folds relative to Day 1.

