8.6. Pharmacokinetics

All participants enrolled in Part 1 (dose escalation/food effect) will receive a single dose on Day 1 and then begin continuous dosing after collection of the 72 hour PK sample. The timing of the PK samples may be altered and/or additional PK samples may be obtained at additional points to ensure thorough monitoring.

For details of PK sample collection, please refer to Section 1, [Table 2](#).

Day 1: participants will be administered GSK3368715 as a single oral dose followed by a 72 hour intervention-free period to evaluate PK. PK samples following Day 1 dose will be collected at Pre-dose, 15 ± 5 min, 30 ± 5 min, 1h ± 5 min, 1.5h ± 5 min, 2h ± 10 min, 3h ± 10 min, 4h ± 10 min, 6h ± 30 min, 8h ± 30 min, 12 ± 2h, 24 ± 2h, 48 ± 2h, 72 ± 2 hrs post-dose.

Day 8: PK samples will be collected at Pre-dose, 1.0h ± 5 min, and 4h ± 10 min post-dose.

Day 15: PK samples will be collected at Pre-dose, 30 ± 5 min, 1h ± 5 min, 2h ± 10 min, 3h ± 10 min, 4h ± 10 min, 6h ± 30 min, 8h ± 30 min, 12 ± 2h, and 24 ± 2h (prior to the next dose) post-dose.

PK samples on other visit days should be collected pre-dose only. All pre-dose PK samples at each visit should be collected within 1 hour prior to dose administration.

For details of PK sample collection for the PK/PD cohort in Part 1, please refer to Section 1.3, [Table 3](#).

For details of PK sample collection during the food effect cohort in Part 1, please refer to Section 1.3, [Table 4](#).

Meal times will be recorded on all PK collection days for Part 1 (dose escalation and PK/PD cohort) and on the dosing days (Days 1 and 5) in the food effect cohort.

Whole blood samples of approximately 2 mL will be collected for measurement of GSK3368715 and its metabolites as specified in the SoA. Blood may be collected at additional time points during the study if warranted and agreed upon between the investigator and the sponsor. Instructions for the collection and handling of biological samples will be provided by the sponsor. The actual date and time (24-hour clock time) of each sample will be recorded. Details of PK blood sample collection, processing, storage and shipping, procedures will be provided in study reference manual (SRM).

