9.6.3.2.1. Food Effect Sub-Study

Pharmacokinetic (PK) parameters AUC(0-∞), AUC(0-t) and Cmax will be log-transformed and analyzed separately using a mixed-effects model with fixed-effect term for fed status (fed or fasted), and participant as a random effect. Point estimates and their associated 90% CIs will be constructed for the differences between fed and in fasted state. The point estimates and their associated 90% CIs will be then back transformed to provide point estimates and 90% CIs for the ratios of fed/fasted. Non-parametric methods such as the

Hodges and Lehmann estimator will be used to estimate the median differences between the fed treatments and the fasted state treatments for t_{max} and $t_{1/2}$. An associated 90% CI for the median differences will be constructed.

Based on the US FDA guidance on food-effect bioavailability studies, the absence of a food-effect will be established if the 90% CI of the ratio for C_{max} and AUC, based on log-transformed data, is within the 80 to 125% equivalence limit. Recommendation on the clinical significance of the effect of food will be based on the magnitude of the change and our understanding of the exposure-clinical response relationship. For the evaluation of food effect, t_{max} at fed and fasted status will be presented by participant and dose cohort in tabular and graphical form.

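### The food-effect crossover gives its second dose after 3.0-4.8 half-lives, and its model neither removes residual Period 1 drug nor has a period term: a modest bias and, separately, a loss of precision (minor)

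*Protocol*

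**What the plan says.** **Design.** Section 4.1.1.1 describes a randomised, single-dose, two-period crossover with six participants per sequence: "GSK3368715 dosing (fed then fasted, or fasted then fed) will be separated by at least 3days". Table 4 in section 1.3 schedules the second dose on Day 5, but "the Day 5 dosing (including all PK assessments) may be performed one day earlier (on Day 4"). It lists a pre-dose sample and sampling to 72 h after each of the two doses.

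**Pharmacokinetics.** Section 2.2.1.5 reports that the drug "declines bi-exponentially with a mean terminal elimination half-life of 20-24 hours", with a peak at about 1 h. It also reports that "mean AUC was up to 2-4 fold higher on Day 15 as compared to Day 1", and 6-7 fold accumulation in some participants.

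**Analysis.** Section 9.6.3.2.1 analyses log AUC and log Cmax "using a mixed-effects model with fixed-effect term for fed status (fed or fasted), and participant as a random effect". Absence of a food effect requires the 90% CI of the fed/fasted ratio to lie within 80-125%. Neither document mentions a period term, a sequence term or a use for the Period 2 pre-dose concentration.

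**Who is analysed.** A note to Table 4 states: "Any participant who experiences vomiting at or between 0.25-3 h will be removed from statistical analysis of PK comparability" in the fasted and fed states. Replacement in 4.1.1.1 covers only dose reduction or discontinuation within 48 h of dosing.

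**Dosing text.** Section 8.6 states: "All participants enrolled in Part 1 (dose escalation/food effect) will receive a single dose on Day 1 and then begin continuous dosing after collection". The sample meant is the one at 72 h. Table 4 shows a second single dose and daily dosing from Day 9.

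**Status.** SAP section 2.1 states that the food-effect analysis will not be done, because enrolment ended early.

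**The concern.** A crossover compares each participant with himself or herself. That works only if Period 1 drug has gone before Period 2, or if the analysis allows for what remains. Here some drug remains and the analysis does not allow for it. Section 5.1 of the protocol uses five terminal half-lives as its example of elimination time, in the contraception criterion. On 20-24 h that is 100-120 h, longer than the 72-96 h allowed here.

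Two things could go wrong, and they are distinct. Residual drug adds to Period 2 exposure in proportion to Period 1 exposure, so the larger fed exposure spills into the fasted period by more than the reverse, and the ratio shrinks. In addition, Period 2 is raised for everyone. Without a period term, that shift is treated as random error.

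Section 4.2 says the result can be used to change dosing instructions in this and future studies, so both the estimate and the CI matter.

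**Working it through.** **1. The plan's own figure.** Section 9.2 gives 80% power with 12 participants at a 10% significance level, CV 0.206, a true ratio of 1 and limits 0.80-1.25. Two one-sided tests on the log scale, with within-participant SD = sqrt(ln(1 + 0.206²)) and SE = SD × sqrt(2/12), give 80.1% at one-sided 0.10. The decision rule is a 90% CI, which is one-sided 0.05 per test. That gives 61.5% on 11 df (the planned model) and 60.6% on 10 df (with a period term). These are the no-carry-over baselines used below. The mismatch with 80% is a separate matter.

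**2. Residual drug.** With one-compartment decline, the share of a dose's AUC still to come at time T is c = 2^(-T/half-life).

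| Second dose | Half-life 20 h | Half-life 24 h |
|---|---|---|
| Day 4 (72 h) | 3.6 half-lives, c = 8.2% | 3.0 half-lives, c = 12.5% |
| Day 5 (96 h) | 4.8 half-lives, c = 3.6% | 4.0 half-lives, c = 6.3% |

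Decline is bi-exponential, so at a given terminal half-life these are upper bounds, ignoring the short absorption phase.

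**3. Accumulation.** Under linear kinetics and once-daily dosing, the accumulation ratio is 1/(1 - 2^(-24/half-life)). That is 1.77 at 20 h and 2.00 at 24 h. A 4-fold ratio would need an effective half-life of 24 × ln 2 / -ln(1 - 1/4) = 58 h. Then c = 0.75³ = 42% on Day 4 and 0.75⁴ = 32% on Day 5.

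**4. Effect on the AUC ratio.** For a true ratio R, the fasted-then-fed sequence shows R + c, and the fed-then-fasted sequence shows R/(1 + cR). With equal sequences the estimate is the geometric mean, sqrt(R(R + c)/(1 + cR)).

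| c | R = 0.80 | R = 1.00 | R = 1.25 | R = 1.43 |
|---|---|---|---|---|
| 3.6% | 0.81 | 1.00 | 1.24 | 1.41 |
| 6.3% | 0.81 | 1.00 | 1.23 | 1.40 |
| 8.2% | 0.81 | 1.00 | 1.23 | 1.39 |
| 12.5% | 0.82 | 1.00 | 1.22 | 1.37 |

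If c were 32-42%, a true 1.25 would read 1.18-1.17.

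**5. Effect of the missing period term.** At R = 1 the within-participant fed-minus-fasted log difference is shifted by +ln(1 + c) in one sequence and -ln(1 + c) in the other. At 6/6 the mean is unchanged, but the spread grows. The SD of the differences is sqrt(2 × ln(1 + 0.206²)) = 0.288, and ln(1.125) = 0.118. The CI is therefore wider by a factor of about sqrt(0.288² + 0.118² × 12/11)/0.288 = 1.09. At c = 6.3% the factor is 1.02.

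Simulated chance of the 90% CI lying within 80-125% (6+6, CV 0.206, 200,000 runs, carry-over as a common shift):

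| True ratio | c | Planned model | With period term |
|---|---|---|---|
| 1.00 | 0 | 61.5% | 60.6% |
| 1.00 | 6.3% | 59.0% | 60.5% |
| 1.00 | 12.5% | 52.9% | 60.5% |
| 1.25 | 0 | 5.0% | 5.0% |
| 1.25 | 12.5% | 6.6% | 8.6% |

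The levels depend on how carry-over is modelled. If it follows each participant's own Period 1 exposure, random variation included, Period 2 partly repeats Period 1. The R = 1 figures at 12.5% then become 67% and 76%, and the R = 1.25 figures 6.9% and 9.3%. The gap of about 8 points at R = 1 is the same in both versions.

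**6. Unequal sequences.** If exclusions leave 7/5 and c = 12.5%, omitting the period term shifts the log ratio by (7 - 5)/12 × 0.118 = 0.020, about 2%, in either direction according to which sequence is larger.

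**The case against.** - **A reader might infer that the missing period term causes the pull towards 1.** It does not when sequences are balanced. The point estimate is the same with or without it, and the wider CI works against declaring no food effect. Adding the term alone leaves the bias and raises the false no-effect rate.
- **A reader might combine the 2-4 fold or 6-7 fold accumulation with the 20-24 h half-life and reach a much larger carry-over.** Under linear kinetics those figures cannot coexist, because that half-life caps accumulation at about 2-fold. The excess may mean slower elimination or clearance that changes with time, and the documents do not say which. The 48 h half-life in 4.3.1 is a preclinical prediction that the human data have replaced.
- **The protocol expects no substantial food effect (4.3.2).** At a ratio of 1 there is no bias, so this objection stands against the first consequence. The loss of precision remains.
- **Day 5 is the scheduled day.** This also stands. Most of the harm is on Day 4, which Table 4 offers as an accommodation.
- **Cmax should be affected less.** A trough at 72-96 h is set against a peak near 1 h, so this is reasonable, but the documents do not allow it to be computed.
- **A reader might infer that 8.6 would ruin Period 2.** The same section refers food-effect sampling to Table 4 and names Days 1 and 5 as the dosing days. It is a contradiction to resolve, not evidence that sites would skip Period 2.
- **The protocol leaves details to the RAP, and bases the clinical recommendation on the magnitude of change.** But the RAP (the SAP) drops the analysis, so the model in 9.6.3.2.1 is the only one on record.

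**Conclusion.** The concern holds in a limited form, and its severity is minor. On the stated half-life, residual drug moves a true AUC ratio of 1.25 to about 1.24-1.22, does not bias a ratio of 1, and raises the false no-effect rate at 1.25 from 5% to at most about 7%. Separately, at 12.5% carry-over the missing period term costs about 8 percentage points in the chance of correctly concluding that food has no effect. On Day 5 the cost is 1.5 points or less.

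These sizes assume linear kinetics, one-compartment residuals as upper bounds, CV 0.206 and 6/6 allocation. A larger bias requires the further assumption that accumulation above 2-fold reflects slower elimination.

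No reported result is affected, because the SAP does not carry out this analysis. The point applies to the protocol plan and to any later study that reuses it.

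**What to change.** In 9.6.3.2.1:

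- Before deriving Period 2 Cmax and AUC, subtract the Period 1 residual: the Period 2 pre-dose concentration, decayed with that participant's Period 1 terminal rate constant.
- Fit sequence, period and fed status as fixed effects, with participant within sequence as random.

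Both are needed. Subtraction removes the bias (with the residual fully removed, 1.25 reads 1.25 and the error returns to 5.0%). The period term protects precision and removes the shift from unequal sequences.

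The cost is one or two model degrees of freedom (61.5% to 60.6% if there is no carry-over at all) and one programming step on samples already scheduled. The subtraction relies on an estimated individual terminal slope, so it adds a little error of its own.

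Reconcile the continuous-dosing sentence in 8.6 with Table 4 and 4.1.1.1.
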